4.3 Selection of Study Population

This will be a single site study conducted at the Mirpur field site by the icddr,b. The first part (Part A) will enroll a total of 45 adult participants (30 vaccinees and 15 placebos) into one Cohort. The second part (Part B) will enroll a total of 150 toddlers (24-29 months) into 6 separate cohorts to be recruited in step-wise

fashion. Each cohort will enroll 25 toddlers (15 vaccinees and 10 placebos). The third part (Part C) will enroll a total of 100 younger children (12-23 months) into 4 separate cohorts in a step-wise fashion. Each cohort will enroll 25 younger children (15 vaccinees and 10 placebos). The fourth part (Part D) will enroll a total of 200 infants (6-11 months) into 5 separate cohorts to be recruited in a step-wise fashion. Each cohort will enroll 40 infants (30 vaccinees and 10 placebos). Toddlers, younger children and infants will only be enrolled if their parents are fully informed about the study and provide consent for their child's participation.

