4.4.2 Method of Assigning Participants to Treatment Groups (Randomization)

The randomization scheme will be generated and maintained by the Statistical Data Coordinating Center (SDCC) at the Emmes Corporation, Rockville, MD. Randomization will occur manually on the day participants are to receive their first study vaccination, after confirmation of eligibility and immediately prior to immunization. The unblinded study pharmacist or member of the IP formulation team will be provided with the treatment assignment codes for preparation of the vaccine or placebo to be given to each participant. The unblinded study pharmacist (or designee) will maintain the treatment code list in a secure place. Each participant's treatment assignment will be entered into the AdvantageEDCSM system at Emmes after product administration has occurred.

Eligible participants were randomized and assigned as shown below. The doses shown in **bold** are the highest safe doses chosen by the IPST. Where appropriate, all tables and figures will report the actual dose received.

- Part A: Adults 1:1:1 ratio Cohort A1
 - Full dose ETVAX only
 - Full dose ETVAX + 10 μg dmLT
 - o Placebo
- Part B: toddlers aged 24 59 months,
 - o Cohort B1 3:2 ratio
 - 1/4 dose ETVAX only
 - Placebo

- o Cohort B2 3:2 ratio
 - 1/2 dose ETVAX only
 - Placebo
- Cohort B3 3:2 ratio
 - Full dose ETVAX only
 - Placebo
- o Cohort B4 3:2 ratio
 - Highest safe dose ETVAX (1/2 dose) + 2.5μg dmLT
 - Placebo
- Cohort B5 3:2 ratio
 - Highest safe dose ETVAX (1/2 dose) + 5μg dmLT
 - Placebo
- Cohort B6 3:2 ratio
 - Highest safe dose ETVAX (1/2 dose) + 10μg dmLT
 - Placebo
- Part C: younger children aged 12 23 months,
 - o Cohort C1 3:2 ratio
 - 1/4 dose ETVAX only
 - Placebo
 - o Cohort C2 3:2 ratio
 - 1/2 dose ETVAX only
 - Placebo
 - Cohort C3 3:2 ratio
 - Highest safe dose ETVAX (1/2 dose) + 2.5µg dmLT
 - Placebo
 - o Cohort C4 3:2 ratio
 - Highest safe dose ETVAX (1/2 dose) + 5µg dmLT
 - Placebo
- Part D: infants aged 6 11 months,
 - Cohort D1 3:1 ratio
 - 1/8 dose ETVAX only
 - Placebo
 - O Cohort D2 3:1 ratio
 - 1/4 dose ETVAX only
 - Placebo
 - o Cohort D3 3:1 ratio
 - 1/2 dose ETVAX only
 - Placebo
 - O Cohort D4 3:1 ratio
 - Highest safe dose ETVAX (1/4 dose) + 2.5μg dmLT
 - Placebo
 - o Cohort D5 3:1 ratio
 - Highest safe dose ETVAX (1/4 dose) + 5µg dmLT
 - Placebo

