A logistic regression analysis will be presented to look at the proportion of vomiting after any ETVAX dose, with covariates for sex, age group (i.e., cohort's B, C and D), dose and adjuvant in the model. The age group categories will correspond with cohorts B, C and D: 6-11 months, 12-23 months, and 24-59 months, respectively. Results will be summarized for all vaccinated children in Table 14.3.1.6.1 and all children in Table 14.3.1.6.2.

The primary purpose of the statistical comparisons is to screen out potential solicited reactogenicity events that need further clinical evaluation. Therefore, they are not considered formal statistical hypothesis tests and it is acknowledged that there will be inflated Type I errors (i.e., inflated false statistical significances) from performing multiple unadjusted comparisons.

Solicited adverse events by participant will be presented in Listings 16.2.7.1(a)(b)(c)(d).

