Elevated Oral Temperature	XX	XX.X	0.xxx	XX	XX.X	0.xxx	XX	XX.X	0.xxx	XX	XX.X	0.xxx
Vomiting	XX	XX.X	0.xxx	XX	XX.X	0.xxx	XX	XX.X	0.xxx	XX	XX.X	0.xxx
Loose stools	XX	XX.X	0.xxx	XX	XX.X	0.xxx	XX	XX.X	0.xxx	XX	XX.X	0.xxx
Diarrhea	XX	XX.X	0.xxx	XX	XX.X	0.xxx	XX	XX.X	0.xxx	XX	XX.X	0.xxx
Acute systemic allergic reaction	XX	XX.X	0.xxx	XX	XX.X	0.xxx	XX	xx.x	0.xxx	XX	XX.X	0.xxx

N = Number of participants in the Safety population; n = Number of participants with a symptom reported post-vaccination.

^a P-value is from a Fisher's exact test, testing the treatment vs placebo.

TABLE 14.3.1.6.1: Univariate and Adjusted Odds of Vomiting after any ETVAX Dose (Day 0) Among Vaccinated Children 6 to 59 Months of Age

			Logistic Reg	gression: OR (95% CI)
Variable	Vomiteda	No vomiting	Univariate	Adjusted
Sex				
Female	n (%) ^b	n	OR (95% CI)	OR (95% CI)
Male	n (%)	n	1	1
Age (months)				
6 to 11				
12 to 23				
24 to 59			1	1
dmLT (mcg)				
0				
2.5				
5.0				
10.0			1	1
Dose ^c				
1/8				
1/4				
1/2			1	1

^aMild or greater vomiting after first, second, or both doses on day 0.

^bn (percent of row total)

^cExclude full dose recipients (n=5) from analysis.

TABLE 14.3.1.6.2: Univariate and Adjusted Odds of Vomiting after any ETVAX Dose (Day 0) Among All Children 6 to 59 Months of Age

			Logistic	Regression
Variable	Vomited ^a	No vomiting	Univariate	Adjusted
Sex				
Female	n (%) ^b	n	OR (95% CI)	OR (95% CI)
Male	n (%)	n	1	1
Age (months)				
6 to 11				
12 to 23				
24 to 59			1	1
Dose ^c				
ETVAX				

Placebo

^aMild or greater vomiting after first, second, or both doses on day 0.

^bn (percent of row total)

^cExclude full dose recipients (n=5) from analysis.

TABLE 14.3.1.7a:

Number and Percentage of Participants Experiencing Unsolicited Adverse Events with 95% Confidence Intervals by MedDRA® System Organ Class and Preferred Term, and Treatment Group - Adults

			Place (N=X		ET	VAX I	Full Dose XX)		AX Ful 0 μg dr (N=X			oined Va (N=XX)	
MedDRA® System Organ Class	MedDRA® Preferred Term	n	n % (95% CI)				(95% CI)	n	%	(95% CI)	n	%	(95% CI)
Any SOC	Any PT		n /0 (9370 C1)										
[SOC 1]	Any PT												
	[PT 1]												
	[PT 2]												
[SOC 2]	Any PT												
	[PT 1]												
	[PT 2]												

N= Number of participants in the Safety Population. A participant is only counted once per preferred term and system organ class.

TABLE 14.3.1.7b:

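### Table 14.3.1.6.1 uses 10 µg dmLT, planned for only 15 children, as the reference level, so it does not print the adjusted odds ratios of 2.5 and 5 µg against ETVAX alone

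*SAP*

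**What the plan says.** SAP section 9.1.1 plans a logistic regression for vomiting in the children, "with covariates for sex, age group (i.e., cohort's B, C and D), dose and adjuvant in the model". It names the covariates but no reference levels. These appear only in a shell in Appendix I, Table 14.3.1.6.1, which carries the title "Univariate and Adjusted Odds of Vomiting after any ETVAX Dose (Day 0) Among Vaccinated Children 6 to 59 Months of Age". That shell lists dmLT at 0, 2.5, 5.0 and 10.0 mcg and prints 1 in the univariate and adjusted columns of the 10.0 row. Sex, age and antigen dose also take their last row as reference (male, 24 to 59 months, 1/2 dose), so the 1 on the 10.0 row looks like a convention and not a misplaced entry.

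Section 4.4.2 gives one paediatric arm with that adjuvant dose, Cohort B6: "Highest safe dose ETVAX (1/2 dose) + 10μg dmLT". Parts C and D stop at 5 µg. The adults of Cohort A1 who received 10 µg are outside this 6 to 59 month model.

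The other planned tests of solicited events (section 9.1.1 and Tables 14.3.1.5a to d) compare single or pooled vaccine arms with placebo. Table 14.3.1.6.2 has no dmLT variable.

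**The concern.** An adjuvant term in a reactogenicity model is there to show whether adding dmLT changes the odds of vomiting compared with the same vaccine without it. Section 2.1 names the safety profile of dmLT as a purpose of the study, and reactogenicity is a primary endpoint in section 3.2.1. This regression is the only planned solicited-event comparison that could answer the question. With 10 µg as reference, the printed rows answer a different one: how 0, 2.5 and 5 µg each compare with 10 µg. All of them share the imprecision of the smallest cell, and all of them fail together if that cell has no event.

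**Working it through.** **The plan's own figures.** The SAP gives no figure for this model, but section 5 gives detection chances for groups of 15, the size of Cohort B6. With 1 − (1 − p)^15:
- p = 10.3%: 0.804, stated as about 80%.
- p = 14.3%: 0.901, stated as about 90%.
- Zero-event one-sided 95% upper bound: 1 − 0.05^(1/15) = 18.1%, stated as about 18%.

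All three reproduce.

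**Planned vaccinees per dmLT level.** Section 4.3 gives 15 vaccinees per cohort in Parts B and C and 30 in Part D. Section 4.4.2 gives the arms. Cohort B3 (full dose) is left out, because the shell excludes full-dose recipients.
- 0 µg: B1, B2, C1, C2 (15 each) and D1, D2, D3 (30 each) = 60 + 90 = 150.
- 2.5 µg: B4, C3, D4 = 15 + 15 + 30 = 60.
- 5 µg: B5, C4, D5 = 15 + 15 + 30 = 60.
- 10 µg: B6 = 15.
- Total 285. The reference level holds 15/285, about 5%.

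**Precision, univariate.** With an equal assumed vomiting rate p in both groups, SE(log OR) = √[1/(n₁p(1−p)) + 1/(n₂p(1−p))]. At p = 10%, p(1−p) = 0.09:
- 60 against 15 (2.5 or 5 µg against 10 µg): √(0.185 + 0.741) = 0.962. The 95% interval runs from the estimate divided by 6.59 to the estimate times 6.59.
- 60 against 150 (2.5 or 5 µg against 0 µg): √(0.185 + 0.074) = 0.509, multiplier 2.71.

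The ratio of the two SEs, √[(1/60 + 1/15)/(1/60 + 1/150)] = 1.89, does not depend on p. For p from 5% to 30% the multipliers run from 13.4 to 3.44 against 10 µg and from 3.95 to 1.92 against 0 µg. The shell's footnote gives only 5 full-dose recipients, although B3 was planned with 15 vaccinees. If up to 15 B3 children count at 0 µg, the ratio is 1.89 to 1.91.

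**Precision, adjusted.** 600 trials were simulated with the planned arms and a logistic model in sex, age group, antigen dose and dmLT level, assuming 10% vomiting without dmLT and an odds ratio of 3 at every dmLT level. The median SE of the log odds ratio was 0.44 for 5 against 0 µg and 0.76 for 5 against 10 µg.

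**Chance of an empty reference cell.** (1 − p)^15, where p is an assumed B6 vomiting rate:
- 5%: 0.46
- 10%: 0.21
- 15%: 0.09
- 20%: 0.03

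This is a separate scenario from the simulation. There the B6 odds are 3 × 0.10/0.90 = 1/3, so p = 25% and the chance is 0.75^15, about 1%. For the 150 children at 0 µg, the chance of no event is below 0.001 even at a 5% rate.

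**The case against.** The strongest reply is that a reference level is only a parameterisation. The likelihood, the fitted risks and the overall dmLT effect are the same whichever level is chosen. Section 9.1.1 says that the solicited-event comparisons screen for events needing further evaluation and are not formal hypothesis tests, and the table prints odds ratios with intervals and no p-values. All of this stands. The point concerns which exploratory estimates are printed and how precise they are, not the validity of the model.

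Four stronger readings should be resisted:
- A reader might infer that the contrasts with 0 µg are lost altogether. They are not. The shell prints the counts with and without vomiting for each dmLT level, so the univariate odds ratios and intervals can be rebuilt. An adjusted point estimate is the ratio of two printed odds ratios. Only its confidence interval is out of reach. That interval matters because dmLT level is entangled with age and antigen dose across the cohorts.
- A reader might infer that an adjuvant effect would be hidden. Tables 14.3.1.1(b) to (d) give vomiting percentages with 95% intervals for each arm and for the combined groups with and without dmLT. What is missing is a direct comparison.
- A reader might call it lost power when the 2.5 and 5 µg rows seldom differ from 10 µg under an equal effect at all levels. Those contrasts are truly null in that case, so their rejection rate is a false-positive rate.
- A reader might expect the change to cure an empty B6 cell. It does not: 10 against 0 µg would still lack a finite maximum-likelihood estimate. The 2.5 and 5 µg rows would be unaffected.

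**Conclusion.** The point holds as a reporting fault in an exploratory safety table. The shell sets as reference the smallest dmLT level, confined to one age group and one antigen dose, and so leaves out the adjusted comparisons of 2.5 and 5 µg with ETVAX alone. The SAP gives no reason for choosing 10 µg and plans no other solicited-event comparison of ETVAX with and without dmLT. The cost in precision is an SE larger by a factor of about 1.9 in the univariate case at equal rates, and of about 0.76/0.44 = 1.7 in the adjusted case. There is also a real chance of an inestimable dmLT block if vomiting in B6 is uncommon. Group sizes are planned and not actual. The vomiting rates and the odds ratio of 3 are assumptions, because the SAP states none. No conclusion rule or analysis population depends on this choice, so the consequence is modest, but the correction is almost free.

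**What to change.** In Table 14.3.1.6.1, move the 1 in the dmLT block to the 0 mcg row and report 2.5, 5 and 10 µg each against 0 with 95% confidence intervals, univariate and adjusted. State the reference level in section 9.1.1. Add that Firth or exact logistic regression will be used if a dmLT level has no events. The reference change costs one option in the program and one moved cell in the shell. The fallback adds one sentence and, if triggered, an alternative fit. No new data are needed.

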9 SAFETY EVALUATION

9.1 Adverse Events

All safety analyses will be presented using the Safety population.

Any medical condition that is present at the time that the participant is screened will be considered baseline and not reported as an AE, unless it worsens in severity or increases in frequency during the study. When calculating the incidence of solicited and unsolicited adverse events (i.e., on a per participant basis), each participant will be counted once and any repetitions of solicited and unsolicited adverse events within a participant will be ignored; the denominator will be the total population size. All adverse events reported will be included in the summaries and analyses.

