9.1.2 Unsolicited Adverse Events

The proportion of participants reporting at least one unsolicited adverse event will be summarized by MedDRA system organ class and preferred term for each treatment group and overall. Denominators for percentages are the number of participants in the Safety population. A 95% CI calculated using Clopper-Pearson methodology from a binomial distribution (SAS Proc Freq with a binomial option) will be presented for each MedDRA system organ class and preferred term (Tables 14.3.1.7(a)(b)(c)(d))

Unsolicited adverse events by participant will be presented in Listings 16.2.7.2(a)(b)(c)(d).

The following summaries for unsolicited adverse events will be presented by treatment group:

- Participant level summary of maximum severity and relationship to study product by MedDRA SOC and PT (Tables 14.3.1.8.1(a)(b)(c)(d));
- Participant level summary of related unsolicited events by maximum severity, MedDRA SOC and PT (Tables 14.3.1.8.2(a)(b)(c)(d));
- Participant incidence of unsolicited adverse events over time by MedDRA SOC and PT (Days 1-8, Days > 8) (Tables 14.3.1.9.1(a)(b)(c)(d));
- Participant incidence of related unsolicited adverse events over time by MedDRA SOC and PT (Days 1-8, Days > 8) (Tables 14.3.1.9.2(a)(b)(c)(d));
- Total frequency of adverse events over time by MedDRA SOC and PT (Days 1-8, Days > 8) (Tables 14.3.1.10(a)(b)(c)(d));
- Participant listing of non-serious adverse events of moderate or greater severity (Tables 14.3.2.2(a)(b)(c)(d));
- Bar chart of the frequency of events for non-serious adverse events by maximum severity and MedDRA SOC (Figures 14.3.1.11(a)(b)(c)(d));
- Bar chart of the percent of participants reporting a non-serious adverse event by maximum severity and MedDRA SOC (Figures 14.3.1.12(a)(b)(c)(d));
- Bar chart of the frequency of any adverse event by maximum severity (Figures 14.3.1.13(a)(b)(c)(d));
- Bar chart of the percent of participants of any adverse event by maximum severity (Figures 14.3.1.14(a)(b)(c)(d));
- Bar chart of the frequency of non-serious adverse events by relationship to treatment and MedDRA SOC (Figures 14.3.1.15(a)(b)(c)(d));

- Bar chart of the percent of participants of non-serious adverse events by relationship to treatment and MedDRA SOC (Figures 14.3.1.16(a)(b)(c)(d));
- Bar chart of the frequency of any adverse event by relationship to treatment (Figures 14.3.1.17(a)(b)(c)(d)).

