(highest safe dose) + 10 µg dmLT, Combined ETVAX + dmLT, Combined Vaccine.

TABLE 14.3.1.9.1c:

Number and Percentage of Participants Experiencing Unsolicited Adverse Events by MedDRA® System Organ Class and Preferred Term, Days Post Vaccination and Treatment Group - Young Children (12 - 23 Months)

			Pl	acebo		E	ΓVAX 1/	4 Dose		E	TVAX 1	/2 Dose		Comb	oined ET	TVAX A	Alone
MedDRA® System Organ	MedDRA®		s 0-7 =X)	Days (N=		Day (N=		Days (N=		Days 1 (N=		Days (N=			s 0-7 =X)	Day (N=	
Class	Preferred Term	n	%	N	%	n	%	n	%	n	%	n	%	n	%	n	%
Any SOC	Any PT																
[SOC 1]	Any PT																
	[PT 1]																
	[PT 2]																
[SOC 2]	Any PT																
	[PT 1]																
	[PT 2]																

Programming Note: Continue with the following treatments: ETVAX

(highest safe dose) + $2.5\mu g$ dmLT, ETVAX

(highest safe dose) + 5 µg dmLT, Combined ETVAX + dmLT, Combined Vaccine.

TABLE 14.3.1.9.1d:
Number and Percentage of Participants Experiencing Unsolicited Adverse Events by MedDRA® System Organ Class and Preferred Term, Days Post Vaccination and Treatment Group - Infants (6 - 11 Months)

			Pl	acebo		E'	TVAX 1/	8 Dose		E	TVAX 1	/4 Dose		E	TVAX	1/2 Dos	e
MedDRA® System Organ	MedDRA®		s 0-7 =X)	Days (N=		Day (N=		Days (N=		Days (N=		Days (N=			s 0-7 =X)	Day (N=	
Class	Preferred Term	n	%	N	%	n	%	n	%	n	%	n	%	n	%	n	%
Any SOC	Any PT																
[SOC 1]	Any PT																
	[PT 1]																
	[PT 2]																
[SOC 2]	Any PT																
	[PT 1]																
	[PT 2]																

Programming Note: Continue with the following treatments: Combined ETVAX Alone, ETVAX

(highest safe dose) + $2.5\mu g$ dmLT, ETVAX

(highest safe dose) + 5 µg dmLT, Combined ETVAX + dmLT, Combined Vaccine.

TABLE 14.3.1.9.2a:
Number and Percentage of Participants Experiencing Related Unsolicited Adverse Events by MedDRA® System Organ Class and Preferred Term, Days Post Vaccination and Treatment Group - Adults

			Pl	acebo		ET	TVAX F	ıll Dose			TVAX F + 10 μg			C	ombined	l Vaccii	1e
MedDRA® System Organ Class	MedDRA®		s 0-7 =X)	Days (N=		Days (N=)		Days (N=		Days (N=		Days (N=			s 0-7 =X)	Day (N=	
	Preferred Term	n	%	N	%	n	%	n	%	n	%	n	%	n	%	n	%
Any SOC	Any PT																
[SOC 1]	Any PT																
	[PT 1]																
	[PT 2]																
[SOC 2]	Any PT																
	[PT 1]																
	[PT 2]																

TABLE 14.3.1.9.2b:

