(highest safe dose) + $2.5\mu g$ dmLT, ETVAX

(highest safe dose) + $5 \mu g dmLT$, Combined ETVAX + dmLT, Combined Vaccine.

TABLE 14.3.1.10a:
Number of Unsolicited Adverse Events by MedDRA® System Organ Class and Preferred Term,
Days Post Vaccination and Treatment Group - Adults

		Pla	acebo	ETVAX F	ull Dose	ETVAX F + 10 μg		Combined	l Vaccine
MedDRA® System Organ	MedDRA®	Days 0-7 (N=X)	Days 8+ (N=X)	Days -0-7 (N=X)	Days 8+ (N=X)	Days 0-7 (N=X)	Days 8+ (N=X)	Days 0-7 (N=X)	Days 8+ (N=X)
Class	Preferred Term	# of Events	# of Events	# of Events	# of Events	# of Events	# of Events	# of Events	# of Events
Any SOC	Any PT								
[SOC 1]	Any PT								
	[PT 1]								
	[PT 2]								
[SOC 2]	Any PT								
	[PT 1]								
	[PT 2]								

TABLE 14.3.1.10b: Number of Unsolicited Adverse Events by MedDRA® System Organ Class and Preferred Term, Days Post Vaccination and Treatment Group - Toddlers (24 - 59 Months)

		Pla	acebo	ETVAX 1	/4 Dose	ETVAX 1	1/2 Dose	ETVAX I	Full Dose
MedDRA® System Organ	MedDRA®	Days 0-7 (N=X)	Days 8+ (N=X)	Days 0-7 (N=X)	Days 8+ (N=X)	Days 0-7 (N=X)	Days 8+ (N=X)	Days 0-7 (N=X)	Days 8+ (N=X)
Class	Preferred Term	# of Events	# of Events	# of Events	# of Events	# of Events	# of Events	# of Events	# of Events
Any SOC	Any PT								
[SOC 1]	Any PT								
	[PT 1]								
	[PT 2]								
[SOC 2]	Any PT								
	[PT 1]								
	[PT 2]								

Note: N=Number of participants in the Safety population. For each time period, a participant is only counted once per preferred term and system organ class.

Programming Note: Continue with the following treatments: Combined ETVAX Alone, ETVAX

(highest safe dose) + $2.5\mu g$ dmLT, ETVAX (highest safe dose) + $5\mu g$ dmLT, ETVAX

(highest safe dose) + 10 µg dmLT, Combined ETVAX + dmLT, Combined Vaccine.

TABLE 14.3.1.10c: Number of Unsolicited Adverse Events by MedDRA® System Organ Class and Preferred Term, Days Post Vaccination and Treatment Group - Young Children (12 - 23 Months)

		Pla	acebo	ETVAX 1	/4 Dose	ETVAX 1	/2 Dose	Combined ET	TVAX Alone
MedDRA® System Organ	MedDRA®	Days 0-7 (N=X)	Days 8+ (N=X)	Days 0-7 (N=X)	Days 8+ (N=X)	Days 0-7 (N=X)	Days 8+ (N=X)	Days 0-7 (N=X)	Days 8+ (N=X)
Class	Preferred Term	# of Events	# of Events	# of Events	# of Events	# of Events	# of Events	# of Events	# of Events
Any SOC	Any PT								
[SOC 1]	Any PT								
	[PT 1]								
	[PT 2]								
[SOC 2]	Any PT								
	[PT 1]								
	[PT 2]								

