Note: N=Number of participants in the Safety population. For each time period, a participant is only counted once per preferred term and system organ class.

Programming Note: Continue with the following treatments: ETVAX

(highest safe dose) $+ 2.5\mu g dmLT$, ETVAX

(highest safe dose) + 5 µg dmLT, Combined ETVAX + dmLT, Combined Vaccine.

TABLE 14.3.1.10d:
Number of Unsolicited Adverse Events by MedDRA® System Organ Class and Preferred Term,
Days Post Vaccination and Treatment Group - Infants (6 - 11 Months)

[figure not shown]
		Pla	acebo	ETVAX 1	/8 Dose	ETVAX 1	/4 Dose	ETVAX	1/2 Dose
MedDRA® System Organ	MedDRA®	Days 0-7 (N=X)	Days 8+ (N=X)	Days 0-7 (N=X)	Days 8+ (N=X)	Days 0-7 (N=X)	Days 8+ (N=X)	Days 0-7 (N=X)	Days 8+ (N=X)
Class	Preferred Term	# of Events	# of Events	# of Events	# of Events	# of Events	# of Events	# of Events	# of Events
Any SOC	Any PT								
[SOC 1]	Any PT								
	[PT 1]								
	[PT 2]								
[SOC 2]	Any PT								
	[PT 1]								
	[PT 2]								

Programming Note: Continue with the following treatments: Combined ETVAX Alone, ETVAX

(highest safe dose) $+ 2.5\mu g$ dmLT, ETVAX

(highest safe dose) + 5 μg dmLT, Combined ETVAX + dmLT, Combined Vaccine.

FIGURE 14.3.1.11a:
Frequency of Non-Serious Adverse Events by MedDRA® System Organ
Class and Maximum Severity - Adults

Programming Note: Continue for all MedDRA System Organ Classes.

FIGURE 14.3.1.11b:

Frequency of Non-Serious Adverse Events by MedDRA® System Organ Class and Maximum Severity - Toddlers (24 - 59 Months)

Programming Note: Use same format as Figure 14.3.1.11b - except use treatment groups: ETVAX 3.5 mL, ETVAX 7mL, ETVAX 14 mL, ETVAX ## + 2.5 μ g dmLT, ETVAX ## + 5 μ g dmLT, ETVAX ## + 10 μ g dmLT, Placebo

FIGURE 14.3.1.11c:

Frequency of Non-Serious Adverse Events by MedDRA® System Organ Class and Maximum Severity - Young Children (12 - 23 Months)

[figure not shown]
Programming Note: Use same format as Figure 14.3.1.11c - except use treatment groups: $ETVAX\ 3.5\ mL$, $ETVAX\ 7mL$, $ETVAX\ ## + 2.5\ \mu g\ dmLT$, $ETVAX\ ## + 5\ \mu g\ dmLT$, Placebo

FIGURE 14.3.1.11d:

Frequency of Non-Serious Adverse Events by MedDRA® System Organ Class and Maximum Severity - Infants (6 - 11 Months)

Programming Note: Use same format as Figure 14.3.1.11d - except use treatment groups: ETVAX 1.75 mL, ETVAX 3.5 mL, ETVAX 7mL, ETVAX ## + 2.5 µg dmLT, ETVAX ## + 5 µg dmLT, Placebo

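### The toddler and young-children event-count tables (14.3.1.10b and c) carry a once-per-participant note, so as written they count participants, unlike the adult and infant tables

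*SAP*

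**What the plan says.** Section 9.1.2 of the SAP lists two summaries of unsolicited events over time, with the same system organ class and preferred term rows. One is participant incidence, in Tables 14.3.1.9.1, whose shells are titled "Number and Percentage of Participants Experiencing Unsolicited Adverse Events by MedDRA® System Organ Class and Preferred Term". The other, in Tables 14.3.1.10, is described as "Total frequency of adverse events over time by MedDRA SOC and PT".

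The 14.3.1.10 shells in Appendix I follow that second description. Their title begins "Number of Unsolicited Adverse Events by MedDRA® System Organ Class and Preferred Term", and every data column is headed as a number of events.

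The note under Tables 14.3.1.10b and 14.3.1.10c then says: "For each time period, a participant is only counted once per preferred term and system organ class". No such note is shown under 14.3.1.10a (adults) or 14.3.1.10d (infants).

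Section 9.1 gives the once-per-participant rule for the calculation of incidence on a per-participant basis: "each participant will be counted once and any repetitions of solicited and unsolicited adverse events within a participant will be ignored". It also says that all reported adverse events will be included in the summaries and analyses.

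**The concern.** In two of the four parts, the note turns an event count into a participant count while the title and columns still say events. A child with three separate respiratory infections in the later window would appear as one event. Two different preferred terms in one child would appear as one event in their shared organ-class row.

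Two things are at stake. For toddlers and young children, the only planned table of event counts by preferred term and time window would merely repeat the n of the incidence table. And in an age-descending trial, where readers will look across the four parts, two tables would count events and two would count participants under the same title.

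**Working it through.** The plan states no figure here to reproduce. The check sets the shells against the text and then sizes the effect under stated assumptions.

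**Step 1: what each place says is counted.**

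| Place in SAP | Unit |
|---|---|
| Section 9.1.2, description of Tables 14.3.1.10 | events |
| Title of Tables 14.3.1.10a to d | events |
| Data columns of Tables 14.3.1.10a to d | events |
| Note under 14.3.1.10b and c | participants, once per term and window |
| Note under 14.3.1.10a and d | none shown |
| Section 9.1, once-per-participant rule | incidence only |
| Section 9.1.2, description of Tables 14.3.1.9.1 | participants |

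The note is the only element of the 14.3.1.10 tables that points to participants. The window labels also differ between Section 9.1.2 (Days 1-8 and beyond) and the shells (Days 0-7 and 8+). That is a separate matter and does not alter this comparison, because the 14.3.1.9.1 and 14.3.1.10 shells use the same windows.

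**Step 2: what the note does to a cell.** Let X be a participant's number of events of one preferred term in one window.

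- Event count: the sum of X over participants.
- Count under the note: the number of participants with X ≥ 1, which is n in the matching cell of Table 14.3.1.9.1.
- Shortfall: the sum of (X − 1) over participants with X ≥ 1.

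With assumed data, 10 participants with 2 episodes each give 10 × 2 = 20 events. The note gives 10, a shortfall of 10. In an event table the preferred-term rows add up to their organ-class row. Under the note they need not.

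**Step 3: can repeats occur under the SAP's rules?** Yes. Section 3.3 starts a new adverse event when more than 24 hours separate loose stools. Section 4.5.1 records symptoms starting after the seven post-vaccination days as adverse events and collects unsolicited events through the Day 42 visit. One child can therefore have two diarrhoea events in the later window.

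**Step 4: reach.** Section 4.3 plans 150 toddlers and 100 young children out of 45 + 150 + 100 + 200 = 495 participants. The note covers 250 of 495.

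**Step 5: size.** The SAP gives no adverse-event rate, so the mean λ per participant, term and window is an assumption. With Poisson counts, the share of events the table would show is (1 − e^(−λ)) / λ.

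| λ (assumed) | Participants with any event, 1 − e^(−λ) | Share shown | Under-count |
|---|---|---|---|
| 0.05 | 4.9% | 0.9754 | 2.46% |
| 0.1 | 9.5% | 0.9516 | 4.84% |
| 0.3 | 25.9% | 0.8639 | 13.61% |
| 1.0 | 63.2% | 0.6321 | 36.79% |

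If events cluster in a few children more than a Poisson model allows, the under-count at a given mean is larger.

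**The case against.** The best defence is that the note looks like wording carried over from the incidence shells. The title, the columns and Section 9.1.2 all say events, the note stands in only two of four sibling tables, and Section 9.1 confines the rule to incidence. A careful programmer might query the note and not apply it. That is a fair guess about conduct, but it leaves the shell contradicting itself: the document supports either count, and the two give different numbers.

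The defence is also right that the effect is contained. Figures 14.3.1.11, 14.3.1.13, 14.3.1.15 and 14.3.1.17 plan event frequencies for every part, and Listings 16.2.7.2a to d show each event with its day post dose and coded terms, so the counts could be rebuilt. Solicited symptoms that start within seven days of vaccination go on the reactogenicity form and are reported as adverse events only if serious (Section 4.5.1). That removes many early repeats of vomiting or loose stools from these tables. For uncommon terms the under-count is small.

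Three stronger readings are tempting, and the SAP does not support them.

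- **That no table counts events.** Tables 14.3.1.10a and d show no such note, so adults and infants, the infants being the largest and youngest part, are not affected.
- **That the primary endpoint is compromised.** Section 3.2.1 defines it as proportions. Participant proportions with exact intervals come from Tables 14.3.1.7, where counting each participant once is correct.
- **That the totals would clash with all the frequency figures.** Figures 14.3.1.11 and 14.3.1.15 cover non-serious events only, so they need not match 14.3.1.10 even when it is counted correctly. The comparison has force only for 14.3.1.13 and 14.3.1.17.

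**Conclusion.** The contradiction is real and confined to Tables 14.3.1.10b and c. Followed literally, their note makes the cells duplicate the n of Tables 14.3.1.9.1b and c, under-counts repeat events in toddlers and young children, and leaves those two parts not comparable with adults and infants.

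That conclusion rests on the text alone. The size cannot be determined from the SAP: the figures of about 2% to 37% depend wholly on assumed means of 0.05 to 1.0 and on the Poisson form. The incidence tables, their confidence intervals, the proportion-based primary endpoint and the listings stand as planned. This is a reporting-shell error of limited weight, worth correcting because the stated rule gives a wrong count and the correction costs almost nothing.

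**What to change.** In Tables 14.3.1.10b and 14.3.1.10c, replace the once-per-participant sentence with: *All events are counted; a participant may contribute more than one event per preferred term and system organ class.* Put the same note under 14.3.1.10a and 14.3.1.10d so that all four parts count alike.

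The once-per-participant note belongs with the incidence tables. It already stands under Tables 14.3.1.7 and can be added to 14.3.1.9.1 and 14.3.1.9.2, where none is shown.

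The cost is a few lines of footnote text. No data collection, test or other planned output changes.
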